7.6 RANDOMIZATION

Patients who meet all the inclusion criteria and none of the exclusion criteria will be randomized 1:1 to either BI 695501 or EU-approved Humira over the 24-week (4-week induction and 20-week maintenance) treatment period after the screening period at Visit 2. The randomization will be stratified by prior exposure to infliximab (Yes/No) and screening SES-CD (<16 or \geq 16).

Randomization will occur on Day 1 (-1/+2) through a standard randomization visit call. Patients will be randomized to each treatment in a 1:1 ratio (BI 695501: EU-approved Humira) using an IRT system.

Boehringer Ingelheim Pharma GmbH & Co. KG, Clinical Trial Supply Unit or a third party appointed by the sponsor will provide the randomization list using a validated randomization number generating system. Access to the randomization code will be controlled and documented. All persons directly involved in the conduct of the trial have no access to the treatment allocation prior to final database lock. The block sizes of the randomization will be documented in the CTR.

7.7 DETERMINATION OF SAMPLE SIZE

The sample size determination is not based on a power calculation, but assures a precise estimation of the relative risk difference. For this trial a precision (distance from observed difference to confidence limit) of 0.115 has been considered necessary and sufficient by the project team. Assuming a response rate of 80%, in both the Humira as well in the BI 695501 treatment arm, the trial will need at least 130 patients (65 per treatment arm).

Page 68 of 93

Proprietary confidential information © 2017 Boehringer Ingelheim International GmbH or one or more of its affiliated companies

Table 7.7: 1Precision of 90% CI

Assumed true response rate		Sample size	Precision ^{\$}	Relative risk (RR)	90% CI
Humira	BI 695501				
85%	85%	65	0.103	1	0.897-1.103
85%	80%	65	0.118	0.941	0.823-1.059
85%	75%	65	0.115	0.882	0.767-0.997
80%	80%	65	0.115	1	0.885-1.115
80%	75%	65	0.120	0.938	0.818-1.058
75%	75%	65	0.125	1	0.875-1.125

⁵Precision is defined as the distance from observed difference to confidence limit. Note that the precision is independent of the actual point estimate.

Calculations performed with nQuery Advisor® 7.0

Table 7.7: 2Precision of 95% CI

Assumed true response rate		Sample size	Precision ⁸	Relative risk (RR)	95% CI
Humira	BI 695501				
85%	85%	65	0.123	1	0.877-1.123
85%	80%	65	0.140	0.941	0.801-1.081
85%	75%	65	0.136	0.882	0.746-1.081
80%	80%	65	0.138	1	0.862-1.138
80%	75%	65	0.143	0.938	0.795-1.081
75%	75%	65	0.149	1	0.851-1.149

^{\$}Precision is defined as the distance from observed difference to confidence limit. Note that the precision is independent of the actual point estimate.

Calculations performed with nQuery Advisor[®] 7.0

Page 69 of 93

Proprietary confidential information © 2017 Boehringer Ingelheim International GmbH or one or more of its affiliated companies

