Name of company:		Boehringer Ingelheim	
Name of finished prod	uct:	NA	
Name of active ingredi	ent:	BI 695501	
Protocol date: 30 May 2016	Trial number: 1297.4		Revision date: 12 Dec 2017
Safety criteria:	assessment, physical	include continuous AE mor l examination, vital signs (blood st (IGRA), 12-lead ECG, injectio	l pressure, pulse rate, and body
Statistical methods:	 BI 695501 with EU- The statistical mode binomial regression exposure to inflixim as fixed, categorical For the primary and endpoints) together interpreted in a desc. The safety population partial) dose of either of AEs will be based AEs with an onset a 	secondary endpoints, point estir with their 90% and 95% CIs	th active Crohn's disease. y endpoint will be a log-linked the stratification factors (prior CD [<16 or \geq 16]) and treatment mates (risk difference for binary will be calculated, but will be tho receive at least one (full or any dosing period. The analysis ergent AEs. That means that all tion up to a period of 10 weeks

09542349-05Trial ProtocolPage 7 of 93Proprietary confidential information © 2017 Boehringer Ingelheim International GmbH or one or more of its affiliated companies

Name of company:		Boehringer Ingelheim	
Name of finished product:	:	NA	
Name of active ingredient	:	BI 695501	
Protocol date:	Trial number:		Revision date:
30 May 2016	1297.4		12 Dec 2017
	will also be considere appropriate trial phas	start before first drug intake and de ed as treatment-emergent. Other Al ses, i.e., screening or post-treatme ted descriptively; in addition RR ar presented.	Es will be assigned to the nt. Safety endpoints and

09542349-05Trial ProtocolPage 8 of 93Proprietary confidential information © 2017 Boehringer Ingelheim International GmbH or one or more of its affiliated companies

FLOW CHART A: SCREENING AND INDUCTION PERIOD

Trial Period	Screen	ing	In	duction		EoT ²	SFU ²
Visit	1	1.1	2 ¹	3	4		
Week	-4 to -2	-1	-1 0 2 4		4	-	14
Day	-28 to -14	-9	1	15	29	-	99
Permitted visit window (days)	-	±2	-1/+2	±1	±1	±3	+7
Informed consent	Х						
Assessment of eligibility	Х	Х	Х				
Demographics	Х						
Medical and surgical history, incl. history of opportunistic infection	Х						
LABS/SAFETY ASSESSMENT	ſS						
Infection screen: hepatitis B							
(HBsAg), hepatitis C (antiHCV), and HIV test (where mandated by local authorities)	Х						
Chest X-ray ³	Х						
TB testing (IGRA) ⁴	X					Х	
CRP/fecal calprotectin	X		X		X	X	
Pregnancy test ⁵	Х		X			Х	Х

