7. STATISTICAL METHODS AND DETERMINATION OF SAMPLE SIZE

7.1 STATISTICAL DESIGN - MODEL

This is a randomized, double-blind, parallel arm, multiple dose, multicenter, multinational, active comparator trial of BI 695501 and EU-approved Humira.

The primary objective of this trial is to compare the clinical efficacy of BI 695501 with EU-approved Humira in patients with active CD at the end of the induction phase at Week 4 by means of the RR.

The primary endpoint (Section 5.1.1) will be analyzed using a log-linked binomial model, which will include stratification factors as covariates (i.e., prior exposure to infliximab [yes/no] and screening SES-CD (<16 or \geq 16).

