7.2 NULL AND ALTERNATIVE HYPOTHESES

This exploratory trial is intended to generate additional data in patients with active CD. Therefore, no formal confirmatory hypotheses for the primary efficacy analysis are defined.

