7.3.1 Primary endpoint analyses

Primary efficacy analysis:

The primary analyses will be performed on the FAS. Patients will be assigned to the treatment they were randomized to receive.

The primary analysis of the observed proportion of patients with a clinical response (CDAI decrease of \geq 70 compared with baseline) at Week 4 will be based on log-linked binomial model. No missing data imputation for primary analysis endpoint need to be taken into account due to FAS definition. However, for pre-specified criteria non-responder imputation (NRI) will be applied (see Section 7.5).

The statistical model can be described as follows:

• (M1) Response to treatment at Week 4 = treatment + prior infliximab exposure + screening SES-CD

This model includes the stratification factor, prior exposure to infliximab, and treatment as fixed, categorical effects and it will be investigated whether the baseline SES-CD will be included as a continuous or as a categorical effect:

- Treatment (BI 695501, EU-approved Humira)
- Prior exposure to infliximab (Yes/No)
- Baseline SES-CD ($<16 \text{ or } \ge 16$)

The relative risk estimate together with its 90% and 95% CI (ratio scale) will be produced.

Further efficacy analyses:

As sensitivity analyses to the primary analysis, the primary endpoint will also be analyzed on the PPS with NRI.

The following explorative hypotheses are not intended to support any biosimilarity claim for BI 695501; however, the framework of non-inferiority testing will be used to compare efficacy of BI 695501 versus EU-approved Humira in a descriptive way.

The following hypotheses will be investigated:

- H_0 : RR of proportion of patients with a clinical response (CDAI decrease of \geq 70 compared with baseline) at Week 4 (BI 695501 versus EU-approved Humira) is less than or equal to 0.76
- H₁: RR of proportion of patients with a clinical response (CDAI decrease of ≥70 compared with baseline) at Week 4 (BI 695501 versus EU-approved Humira) is greater than 0.76

Two-sided 90% CI will be used for the comparison.

The applied margin (0.76 on the ratio scale for CDAI 70) does preserve 39% of the historical effect of adalimumab over placebo (based on a meta-analysis of GAIN and CLASSIC1; see Appendix 10.3 for further details).

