10.3 DETAILS ABOUT THE STATISTICAL CONSIDERATIONS

The purpose of this appendix is to detail the meta-analysis to estimate the expected treatment effect.

The historical treatment effect of Humira was established based on a meta-analysis of studies being representative for the treatment effect of Humira in the intended 1297.4 trial population:

- CLASSIC 1 (R13-2267): a randomized, double-blind, placebo-controlled, dose-ranging trial performed to evaluate the efficacy of adalimumab induction therapies in patients with CD. In this trial, one endpoint was the percentage of patients achieving a 70-point response at Week 4.
- GAIN (R13 2264): a 4-week, randomized, double-blind, placebo-controlled trial performed to determine whether adalimumab induces remission more frequently than placebo in adult patients with CD who have symptoms. One endpoint was also the decrease in CDAI score by 70 points.

The results are detailed in Table 10.3: 1.

	CLASS	IC I	GAIN		
	Ada 160 mg/80 mg	Placebo	Ada 160 mg/80 mg	Placebo	
Number and frequency of patients with 70 points CDAI decrease	45 (59.2%)	27 (36.5%)	82 (51.6%)	56 (33.7%)	
Total number of patients per group	76	74	159	166	

Ada: adalimumab; CDAI: Crohn's Disease Activity Index.

12 Dec 2017

Trial Protocol

Page 83 of 93

Proprietary confidential information © 2017 Boehringer Ingelheim International GmbH or one or more of its affiliated companies

Response rate

The effect size was computed using the Freeman and Tukey method which is used to normalize and variance-stabilize the sampling distribution of proportions. Then the fixed-effects method was used to pool the response rates together. When back-transforming the results and considering inverse-variance weights, the pooled response rate was 54.1% (95% CI from 47.6% to 60.4%).

Non-inferiority margin

As this is an add-on study only, the standard rules for non-inferiority margin selection will not be applied. Instead, the magnitude of preserved historical treatment effect will be used (based on the point estimate rather than confidence interval).

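### Protocol 7.7 sizes the trial on a risk-difference precision of 0.115 but prints it as a confidence interval for the relative risk, overstating RR precision

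*Protocol*

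**What the plan says.** Protocol 7.7 states that the sample size does not come from a power calculation but "assures a precise estimation of the relative risk difference". The target is then given: "For this trial a precision (distance from observed difference to confidence limit) of 0.115 has been considered necessary and sufficient by the project team". With 80% response assumed in both arms, this leads to at least 130 patients, 65 per arm.

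Tables 7.7:1 (90%) and 7.7:2 (95%) list six pairs of response rates, each with a precision, an RR and a CI. At 80/80 the RR is 1, with a 90% CI of 0.885–1.115 and a 95% CI of 0.862–1.138. A note under both tables adds: "Note that the precision is independent of the actual point estimate".

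The effect measure is defined elsewhere. Protocol 7.1 compares the arms "at the end of the induction phase at Week 4 by means of the RR", and 7.3.1 adds: "The relative risk estimate together with its 90% and 95% CI (ratio scale) will be produced". SAP 15.1.3 says the same. The synopsis also names a "risk difference for binary" endpoints, covering the primary and secondary endpoints. Protocol 7.2 states that "no formal confirmatory hypotheses for the primary efficacy analysis are defined". The only threshold is the descriptive RR margin of 0.76 in 7.3.1, read against a two-sided 90% CI.

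**The concern.** The text defines precision as a distance from an observed difference, but the tables attach that distance to a ratio. A risk difference of 0.115 and an RR distance of 0.115 are different quantities: at a common response rate p, the ratio-scale half-width is the difference half-width divided by p, so it is always larger. If the tables hold difference half-widths, their RR intervals belong to neither scale and look tighter than the design can deliver.

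This matters because precision is the only stated reason for 130 patients. A reader would take the tables as the expected width of the interval the trial will report for its primary endpoint.

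**Working it through.** **Inputs.** n = 65 per arm, the six pairs of rates and the printed precisions are from Protocol 7.7. z = 1.645 (90%) or 1.960 (95%). Rates are written Humira/BI 695501.

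**Step 1: reproduce the printed precision.** Difference half-width = z × √[pH(1−pH)/65 + pB(1−pB)/65].

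At 80/80, 90%: 1.645 × √(2 × 0.16/65) = 0.1154, which rounds to the stated 0.115.

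| Rates | 90% computed | 90% printed | 95% computed | 95% printed |
|---|---|---|---|---|
| 85/85 | 0.103 | 0.103 | 0.123 | 0.123 |
| 85/80 | 0.109 | **0.118** | 0.130 | **0.140** |
| 85/75 | 0.1145 | 0.115 | 0.136 | 0.136 |
| 80/80 | 0.1154 | 0.115 | 0.1375 | 0.138 |
| 80/75 | 0.120 | 0.120 | 0.143 | 0.143 |
| 75/75 | 0.125 | 0.125 | 0.149 | 0.149 |

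Five of six rows in each table are risk-difference half-widths. The 85/80 row is not. Table 7.7:1 itself shows something is wrong there: 85/80 is printed as less precise than 85/75 (0.118 against 0.115), although its variance sum is smaller (0.1275 + 0.1600 = 0.2875 against 0.1275 + 0.1875 = 0.3150).

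**Step 2: how the printed intervals were formed.** They are RR ± precision; at 80/80, 1 ± 0.115 = 0.885–1.115. The one exception is 85/75 in Table 7.7:2: 0.882 + 0.136 = 1.018, but 1.081 is printed.

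**Step 3: RR intervals for the same design.** Log-scale large-sample CI = RR × exp(± z × √[(1−pH)/(65pH) + (1−pB)/(65pB)]).

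At 80/80, 90%: √(2 × 0.20/(65 × 0.80)) × 1.645 = 0.1443, so exp(±0.1443) = 0.866–1.155. The distances from 1 are 0.134 and 0.155.

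| Rates | 90% printed | 90% log-scale RR | 95% printed | 95% log-scale RR |
|---|---|---|---|---|
| 85/85 | 0.897–1.103 | 0.886–1.129 | 0.877–1.123 | 0.866–1.155 |
| 85/80 | 0.823–1.059 | 0.824–1.075 | 0.801–1.081 | 0.803–1.103 |
| 85/75 | 0.767–0.997 | 0.763–1.021 | 0.746–1.081 | 0.742–1.050 |
| 80/80 | 0.885–1.115 | 0.866–1.155 | 0.862–1.138 | 0.842–1.188 |
| 80/75 | 0.818–1.058 | 0.802–1.096 | 0.795–1.081 | 0.779–1.129 |
| 75/75 | 0.875–1.125 | 0.847–1.181 | 0.851–1.149 | 0.820–1.220 |

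**Step 4: does the choice of RR method explain 0.115?** No. A symmetric ratio-scale interval at 80/80 has half-width 0.1154/0.80 = 0.144 (90%), and 0.1375/0.80 = 0.172 (95%). At 85/75 the symmetric 90% interval is 0.882 ± 0.129, about 0.754–1.011. Like the log-scale interval, it includes 1, whereas the printed 0.767–0.997 does not.

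**Step 5: what 0.115 on the RR would need at 80/80 (90%).**
- Symmetric: 2 × 0.25 × (1.645/0.115)² = 102.3, so about 103 per arm.
- Log scale, lower limit 0.885: about 91 per arm.
- Log scale, upper limit 1.115: about 115 per arm.

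**Step 6: sensitivity to the response rate.** Appendix 10.3 pools the adalimumab response rate at 54.1% (95% CI 47.6–60.4%). With equal rates in both arms:

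| Rate | 90% difference half-width | 90% log-scale RR CI |
|---|---|---|
| 60.4% | 0.141 | 0.792–1.263 |
| 54.1% | 0.144 | 0.767–1.304 |
| 47.6% | 0.144 | 0.739–1.354 |

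**The case against.** The best defence is that 0.115 is correct on the scale 7.7 defines. It is a distance from an observed difference, the synopsis lists a risk difference for the primary endpoint, and 65 per arm delivers it. On that reading the sample size is sound and only the CI column is mislabelled. This stands as far as it goes, and it is why no change in sample size is asked for. It does not rescue the tables, which label the intervals as RR intervals while 7.1, 7.3.1 and the SAP make the RR the primary measure.

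The consequences are also small. No confirmatory hypothesis exists, and whether an interval excludes 1 is not a planned criterion. In all 12 tabulated rows the printed and log-scale lower limits fall on the same side of 0.76. That is correct.

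Nor is the overstatement uniform. The misprinted 85/75 interval in Table 7.7:2 is wider than the log-scale one, and in both 85/80 rows the printed lower limit is slightly below the log-scale limit. These exceptions come from the two row errors.

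Finally, the documents do not show that 80% is wrong. That is accepted; the missing reason for it is a secondary matter of clarity.

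**Conclusion.** The point holds. The 0.115 is a 90% risk-difference half-width at 80% response, presented as RR precision. At 80/80 the RR interval should read about 0.866–1.155 (90%) and 0.842–1.188 (95%). On a symmetric ratio scale the half-width is 0.144, 25% more than stated. The 85/80 precisions and the 85/75 upper limit in Table 7.7:2 are wrong whichever scale is chosen for the final tables.

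The note that precision does not depend on the point estimate does not carry over to RR intervals. Even for a difference it needs the response rates to be held fixed, since the tables' own 90% half-widths run from 0.103 to 0.125.

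The RR figures assume 65 analysed patients per arm, observed rates equal to the assumed ones, and an unadjusted large-sample interval; the covariate-adjusted log-binomial model may differ somewhat. No decision rule, error rate or analysis is affected. The correction is still worth making, because this precision is the sole stated basis for the sample size.

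**What to change.** Keep 130 patients and take one of two routes in Protocol 7.7:

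1. Replace both tables with log-scale RR intervals (the values in the second table above) and restate the claimed precision as distances of about 0.134 below and 0.155 above an RR of 1 at 80/80, 90%.
2. State that 0.115 is the risk-difference precision at 80% in both arms, and remove the RR-centred intervals.

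The team should say which was meant. If 0.115 was required on the RR, 65 per arm does not provide it, and the text should say that the lower precision is accepted for an exploratory trial.

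On either route:
- Reword the phrase that mixes relative risk and difference.
- Correct the 85/80 precisions to 0.109 and 0.130 if the difference scale is kept.
- Correct the 85/75 upper limit in Table 7.7:2: 1.018 by the table's own arithmetic, about 1.050 as a log-scale RR limit.
- Delete the note on independence from the point estimate, or restrict it to a difference at fixed assumed rates.

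As an optional clarification, give the reason for 80% and add rows at 47.6%, 54.1% and 60.4%, since the tabulated 75–85% lies wholly above the pooled historical estimate in Appendix 10.3.

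The cost is an edit to the text and two tables of 7.7; the available SAP text has no precision table. The stated precision becomes less favourable, but no patients are added and neither endpoint nor analysis changes.

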3.3.2 Inclusion criteria

1. Males and females aged ≥18 and ≤80 years at Screening who have a diagnosis of moderate to severely active CD, confirmed by endoscopy or radiologic evaluation, for

Proprietary confidential information © 2017 Boehringer Ingelheim International GmbH or one or more of its affiliated companies

more than 4 months with evidence of mucosal ulceration. Patients must have all of the following:

- a. CDAI score of \geq 220 and \leq 450
- b. A diagnosis of CD confirmed by ileocolonoscopy during Screening
- c. Presence of mucosal ulcers in at least one segment of the ileum or colon and a SES-CD score ≥7 (for patients with isolated ileal disease SES-CD score ≥4), as assessed by ileocolonoscopy and confirmed by central independent reviewer(s) before randomization
- 2. Anti-TNF naïve patients or patients previously treated with infliximab who had initially responded and who meet one of the following criteria:
 - a. Responded and developed secondary resistance due confirmed anti-infliximab ADA formation, which caused infliximab depletion
 - b. Responded and became intolerant
- 3. Willing to undergo up to 3 endoscopies
- 4. For participants of reproductive potential (males and females¹), a reliable means of contraception has to be used throughout trial participation. Acceptable methods of birth control include, for example, birth control pills, IUDs, surgical sterilization, vasectomized partner, and double barrier method (for example male condom in combination with female diaphragm/cervical cap plus spermicidal foam/gel/film/cream/suppository). All patients (males and females of childbearing potential) must also agree to use an acceptable method of contraception for 6 months following completion or discontinuation from the trial medication.
- 5. Signed and dated written informed consent in accordance with GCP and local legislation prior to admission to the trial

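### The 0.115 precision that justifies 65 patients per arm rests on an unsourced 80% response rate, not reconciled with the 54.1% in Appendix 10.3, where the half-width would be about 0.144

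*Protocol*

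**What the plan says.** Protocol Section 7.7 disclaims power: "The sample size determination is not based on a power calculation". It relies on interval width instead, stating that "a precision (distance from observed difference to confidence limit) of 0.115 has been considered necessary and sufficient by the project team". The 65 per arm (130 in total) follows from one planning rate: "Assuming a response rate of 80%, in both the Humira as well in the BI 695501 treatment arm". Tables 7.7:1 (90% CI) and 7.7:2 (95% CI) vary the response rates between 75% and 85%. The section cites no source for 80% and does not refer to Appendix 10.3.

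Appendix 10.3 says that it details a meta-analysis to estimate the expected treatment effect. It describes its two placebo-controlled adalimumab trials as "studies being representative for the treatment effect of Humira in the intended 1297.4 trial population". For a 70-point CDAI decrease at 160/80 mg it lists 45/76 (59.2%) and 82/159 (51.6%). A separate paragraph headed Response rate pools these to 54.1%, with a 95% CI of 47.6% to 60.4%. The next paragraphs derive the 0.76 margin from pooled risk ratios.

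Section 7.3.1 sets the risk ratio against that margin descriptively: "Two-sided 90% CI will be used for the comparison".

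**The concern.** The protocol holds two very different figures for the same quantity, Week 4 CDAI-70 response on adalimumab 160/80 mg. The lowest tabulated planning rate, 75%, is 14.6 percentage points above the upper confidence limit in Appendix 10.3 (75 − 60.4). No text explains the gap.

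This matters because the half-width is the only support for the sample size. With no confirmatory hypothesis and no power statement, the stated width is what tells a reader how much the trial can show. The variance of a proportion rises as the rate moves from 80% towards 50%. If the true rate is nearer the appendix figure, the interval will be wider than anything in Tables 7.7:1 and 7.7:2 for equal arms. The descriptive comparison with 0.76 would then be less informative than a reader of the tables would expect.

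**Working it through.** **Inputs.** n = 65 per arm, target half-width 0.115 and planning rate 80% (Section 7.7); two-sided 90% CI, z = 1.645 (Section 7.3.1 and Table 7.7:1); historical rates 59.2%, 51.6% and pooled 54.1% (Appendix 10.3).

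**1. Reproduce the plan's figure.** Wald half-width for a risk difference with equal rates: h = 1.645 × √(2p(1 − p)/65).

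- p = 0.80: 1.645 × √(0.32/65) = 0.1154, which matches the stated 0.115.
- The unequal-rate version of this formula also reproduces the 90% rows for 85/85 (0.103), 85/75 (0.115), 80/75 (0.120) and 75/75 (0.125). The 85/80 row does not reproduce (0.109 computed, 0.118 printed), which does not affect this point.

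So this is the protocol's own method, and 0.115 is right at 80% on the difference scale.

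**2. Same formula at the Appendix 10.3 rates.**

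| Response, both arms | 90% half-width | 95% half-width | 90% width relative to 0.1154 |
|---|---|---|---|
| 80% (Section 7.7) | 0.115 | 0.138 | 1.00 |
| 59.2% | 0.142 | 0.169 | 1.23 |
| 54.1% (pooled) | 0.144 | 0.171 | 1.25 |
| 51.6% | 0.144 | 0.172 | 1.25 |

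At the upper confidence limit of 60.4%, h = 1.645 × √(2 × 0.604 × 0.396/65) = 0.141. The half-width is almost flat over this range, so the result hardly depends on which appendix rate is used. For a rate between the two sources, such as 70%, h = 1.645 × √(0.42/65) = 0.132.

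**3. Risk-ratio scale, on which the primary analysis reports.** With equal arms the expected 90% CI is exp(±1.645 × √(2(1 − p)/(65p))).

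- 80%: 0.866 to 1.155
- 59.2%: 0.787 to 1.271
- 54.1%: √(0.918/35.165) = 0.1616, and exp(±0.2658) gives 0.767 to 1.304
- 51.6%: 0.756 to 1.322

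Table 7.7:1 prints 0.885 to 1.115 for 80/80 because it places the difference half-width around a ratio of 1. That is a separate matter. The widening described here appears on either scale.

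**4. Check of the pooled rate.** (45 + 82)/(76 + 159) = 127/235 = 54.0%, in agreement with the stated 54.1%.

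**The case against.** The strongest reply is that Section 7.7 is openly conditional on 80%, and under that condition the figure is correct. That stands: the shortfall arises only if the true rate is near the appendix rates.

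Second, Appendix 10.3 calls the trials representative for the treatment effect, and Section 7.3.1 cites the appendix only for the relative margin against placebo. A trial can represent a relative effect without fixing the absolute response in an all-active trial. This stands in part. Both 80% and the representativeness statement could be true, so that statement need not be withdrawn. But the appendix pools the absolute response under its own heading, separately from the margin, so a reader is entitled to ask why Section 7.7 does not use it.

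Third, the analysis population could raise the rate, because the FAS requires complete baseline and post-baseline CDAI. On the appendix data, reaching 80% that way would mean dropping about 76 of 235 patients, all non-responders (127/0.80 ≈ 159). Patients who discontinue treatment before Week 4 are counted as non-responders, which works the other way.

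Fourth, the trial is exploratory and the 0.76 comparison is descriptive. This limits the consequence but does not remove the conflict, since precision is the stated reason for the sample size.

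A reader might also infer more than the documents support:

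- **That the eligible populations are those of the two historical trials, so that any mix must respond at 51.6% to 59.2%.** Only one trial is identified, by its cited title, as infliximab pre-treated, and the other's prior anti-TNF exposure is not stated. This protocol also restricts pre-treated patients to "patients previously treated with infliximab who had initially responded" and then developed resistance or intolerance, and it requires mucosal ulcers and a minimum SES-CD. Neither restriction is documented for the historical trials.
- **That the sample size must rise.** Holding 0.115 at the appendix rates would take about 198 to 206 patients in total, from n = 2p(1 − p)(1.645/0.115)² per arm. But the documents do not establish that the true rate is near 54%, and Section 11.2 describes serious difficulty in finding patients.

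**Conclusion.** The point holds as an unreconciled conflict over the one planning figure that supports the sample size. At 80% response the stated 0.115 is correct on the difference scale. If response matched Appendix 10.3, the 90% half-width would be 0.142 to 0.144, about 23% to 25% wider. With equal arms at 54.1% the expected 90% CI for the risk ratio would be about 0.77 to 1.30, with its lower end close to the 0.76 margin.

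This assumes 65 evaluable patients per arm, equal true rates and large-sample Wald or log-scale intervals without covariate adjustment. It does not show that 80% is wrong, since the sponsor may have a reason that is not given. It does not invalidate the trial or alter any analysis. It changes what the trial can fairly say in advance about its precision.

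**What to change.** Keep 130 patients. In Protocol Section 7.7:

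1. Add equal-rate rows for about 52%, 54% and 59% to Tables 7.7:1 and 7.7:2. The difference half-widths are 0.144, 0.144 and 0.142 (90%) and 0.172, 0.171 and 0.169 (95%).
2. State that the expected 90% precision is about 0.14 on the difference scale at the Appendix 10.3 rate, and 0.115 only if response is 80%.
3. Refer to Appendix 10.3, and cite the basis for 80% if there is one.

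The representativeness statement in Appendix 10.3 can stay. The cost is protocol wording and a less favourable stated precision, with no extra patients and no change to the analysis.
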